Appendix F. NCCN Risk Categorization: Guidelines for AML Version 2.2016

Risk Category	Cytogenetic
Favorable Risk	Core binding factor: inv(16) or t(16;16) or t(8;21) t(15;17)
Intermediate Risk	Normal cytogenetics +8 alone t(9;11) Other non-defined
Poor Risk	Complex (≥ 3 clonal chromosomal abnormalities) Monosomal karyotype -5,5q-, -7,7q- 11q23-non t(9;11) inv(3),t(3;3) t(6;9) t(9;22)

Appendix G. Tumor Lysis Syndrome Classification

Metabolic Abnormality	Criteria for Classification of Laboratory Tumor Lysis Syndrome*	Criteria for Classification of Clinical Tumor Lysis Syndrome**
Hyperuricemia	Uric acid > 8 mg/dL (475.8 µmol/liter)	N/A
Hyperphosphatemia	Phosphorus > 4.5 mg/dL (1.5 mmol/liter)	N/A
Hyperkalemia	Potassium > 6 mmol/liter	Cardiac dysrhythmia or sudden death probably or definitely caused by hyperkalemia
Hypocalcemia	Corrected calcium < 7.0 mg/dL (1.75 mmol/liter) or ionized calcium < 1.12 mg/dL (0.3 mmol/liter) [#]	Cardiac dysrhythmia, sudden death, seizure, neuromuscular irritability (tetany, paresthesias, muscle twitching, carpopedal spasm, Trousseau's sign, Chvostek's sign, laryngospasm, or bronchospasm), hypotension, or heart failure probably or definitely caused by hypocalcemia***
Acute Kidney Injury [!]	N/A	Increase in the serum creatinine level of 0.3 mg/dL (26.5 µmol/liter) or the presence of oliguria (average urine output of < 0.5 mL/kg/hr over a 6-hour period) [†]

* Laboratory TLS requires two or more metabolic abnormalities must be present during the same 24-hour period within 3 days before the start of therapy or up to 7 days afterward.

** Clinical TLS requires the presence of Laboratory TLS plus one or more findings from the Clinical TLS column.

Corrected calcium = measured calcium level in mg/dL + 0.8 × (4 – albumin in gm/dL).

! Acute kidney injury, unless attributable to another cause, represents clinical TLS even if criteria for laboratory TLS are not satisfied.

*** Not directly or probably attributable to therapeutic agent.

† If no institutional ULN is specified, age/sex ULN creatinine may be defined as follows: > 1 to < 12 years of age, both male and female, 61.6 µmol/L; ≥ 12 to < 16 years, both male and female, 88 µmol/L; ≥ 16 years, female 105.6 µmol/L, male 114.4 µmol/L.

Note: Laboratory tumor lysis syndrome and at least one clinical complication.

Cross reference: Howard SC, Jones DP, Pui CH. The tumor lysis syndrome. N Engl J Med. 2011;364(19):1844-54.

Appendix H. Cell Lines Table

Venetoclax is potent against AML cell lines treated in vitro. AML cell lines were treated with increasing concentrations of venetoclax for 48 hours before assessing cell viability. Venetoclax cell killing IC₅₀ values are shown for each cell line.

Cell Line	Venetoclax IC ₅₀ (μM)	Genetic Lesions
MOLM-13		MLL- and FLT3-mutant
GDM-1		nd
EOL-1		MLL-mutant
HL-60		
MV4-11		MLL- and FLT3-mutant
ML-2		MLL-mutant
SIG-M5		nd
OCI-AML2		nd
MOLM-16		nd
OCI-AML5		nd
THP-1		
Kasumi-1		t(8;21) translocation
KG-1		nd
HNT-34		nd
PL-21		FLT3-mutant
SKM-1		nd
UKE-1		JAK2-mutant
SET-2		JAK2-mutant
HEL		JAK2-mutant
OCI-M2		nd
OCI-AML3		
OCI-M1		nd
NOMO-1		MLL-mutant
ME-1		and inv16

nd = not determined

Cell Line	Venetoclax Combination with 5-Aza
MOLM-13	0
RI-1	0
EOL-1	0
SUP-B15	0
MV4-11	0
ML-2	0
OCI-AML2	0
MOLM-16	0
OCI-AML5	0
KG-1	0
HNT-34	1.0
SKM-1	0
UKE-1	0
SET-2	0
HEL	0
OCI-M2	0
OCI-AML3	0.5
NOMO-1	1.0
KU812	0
PL-21	0.5

0 = additive; 0.5 = weak synergy; 1.0 = strong synergy; -1.0 = antagonism

Appendix I. Sample List of Excluded and Cautionary Medication

Excluded
Strong CYP3A inducers** – avasimibe, carbamazepine, enzalutamine, mitotane, phenytoin, rifampin, St. john's wort
Cautionary, Consider Alternative Medications, Additional Guidance Noted:

Moderate CYP3A inducers** – bosentan, efavirenz, etravirine, modafinil, nafcillin
 
Strong CYP3A inhibitors† – Boceprevir, clarithromycin, cobicistat, conivaptan, danoprevir/ritonavir, elvitegravir/ritonavir, idelalisib,* indinavir, itraconazole, ketoconazole, mibefradil, lopinavir/ritonavir, nefazodone, nelfinavir, paritaprevir/ritonavir combinations, ritonavir, posaconazole, saquinavir, telaprevir, telithromycin, tipranavir/ritonavir, troleandomycin, voriconazole
 
Moderate CYP3A inhibitors‡ – Amprenavir, aprepitant, atazanavir, cimetidine, ciprofloxacin, clotrimazole, crizotinib,* cyclosporine, darunavir/ritonavir, diltiazem,¹ dronedarone, erythromycin, fluconazole, fluvoxamine, fosamprenavir, imatinib,* isavuconazole, tofisopam, verapamil
 
P-gp inhibitors† Amiodarone, captopril, carvedilol, dronedarone, felodipine, propafenone, quercetin, quinidine, ronalzine, ticagrelor

Cautionary

Warfarin and Coumarin derivatives^
 
P-gp substrates Aliskiren, ambrisentan, colchicine, dabigatran etexilate, digoxin, everolimus,* fexofenadine, lapatinib,* loperamide, maraviroc, nilotinib,* ranolazine, saxagliptin, sirolimus,* sitagliptin, talinolol, tolvaptan, topotecan*
 
BCRP substrates Methotrexate,* mitoxantrone,* irrinotecan,* lapatinib,* rosuvastatin, sulfasalazine, topotecan*
 
OATP1B1/1B3 substrates Asunaprevir atrasentan, atorvastatin, cerivastatin, docetaxel ezetimibe, fluvastatin, glyburide, nateglinide, paclitaxel, rosuvastatin, simvastatin acid, pitavastatin, pravastatin, repaglinide, telmisartan, valsartan, olmesartan
 
BCRP inhibitors Gefitinib,* curcumin

* These are anticancer agents that must not be used during study participation.

** If subject requires use of these medications, use with caution and contact AbbVie Medical Monitor or designee (refer to Section 6.1.5) for guidance.

† If subject requires use of these medications, use with caution and reduce the venetoclax dose by at least 4-fold (Table 2). After discontinuation of CYP3A inhibitor, wait for 2 to 3 days before venetoclax dose is increased back to the target dose.

‡ If subject requires use of these medications, use with caution and reduce the venetoclax dose by at least 2-fold (Table 2). After discontinuation of CYP3A inhibitor, wait for 2 to 3 days before venetoclax dose is increased back to the target dose.

^ Closely monitor International Normalized Ratio (INR).

1 Moderate CYP3A inhibitor per venetoclax FDA USPI.

Note that this is not an exhaustive list. For an updated list, see the following link:
<http://www.fda.gov/Drugs/DevelopmentApprovalProcess/DevelopmentResources/DrugInteractionsLabeling/ucm093664.htm>

In addition to the medications listed in this table, subjects receiving venetoclax should not consume grapefruit, grapefruit products, Seville oranges (including marmalade containing Seville oranges) or starfruits.

Appendix J. Recommendations for Initial Management of Electrolyte Imbalances and Prevention of Tumor Lysis Syndrome (TLS)

Abnormality	Management Recommendations
Hyperkalemia (including rapidly rising potassium)	
Potassium ≥ 0.5 mmol/L increase from prior value (even if potassium within normal limits [WNL])	
 • Recheck potassium, phosphorus, uric acid, calcium and creatinine in 1 hour STAT. If further ≥ 0.2 mmol/L increase in potassium, but still $<$ upper limit of normal (ULN), manage as per potassium \geq ULN. Otherwise recheck in 1 hour. • Resume per protocol testing if change in potassium is < 0.2 mmol/L, and potassium $<$ ULN, and no other evidence of tumor lysis. • At discretion of investigator, may recheck prior to hospitalization. If stable or decreased, and still WNL, hospitalization is at the discretion of the investigator. Potassium, phosphorus, uric acid, calcium and creatinine must be rechecked within 24 hours.
Potassium $>$ upper limit of normal	
 • Perform STAT ECG and commence telemetry. • Nephrology (or other acute dialysis service) notification with consideration of initiating dialysis. • Administer Kayexalate 60 g (or Resonium A 60 g). • Administer furosemide 20 mg IV $\times 1$. • Administer calcium gluconate 100 – 200 mg/kg IV slowly if there is ECG/telemetry evidence of life-threatening arrhythmias. • Recheck potassium, phosphorus, uric acid, calcium and creatinine in 1 hour STAT. • If potassium $<$ ULN 1 hour later, repeat potassium, phosphorus, uric acid, calcium and creatinine 1, 2 and 4 hours, if no other evidence of tumor lysis.
Potassium ≥ 6.0 mmol/L (6.0 mEq/L) and/or symptomatic (e.g., muscle cramps, weakness, paresthesias, nausea, vomiting, diarrhea)	
 • Perform STAT ECG and commence telemetry. • Nephrology (or other acute dialysis service) assessment with consideration of initiating dialysis. • Administer Kayexalate 60 g (or Resonium A 60 g). • Administer furosemide 20 mg IV $\times 1$. • Administer insulin 0.1 U/kg IV + D25 2 mL/kg IV. • Administer sodium bicarbonate 1 – 2 mEq/kg IV push. • If sodium bicarbonate is used, rasburicase should not be used as this may exacerbate calcium phosphate precipitation. • Administer calcium gluconate 100 – 200 mg/kg IV slowly if there is ECG/telemetry evidence of life-threatening arrhythmias. Do not administer in same IV line as sodium bicarbonate. • Recheck potassium, phosphorus, uric acid, calcium and creatinine every hour STAT.

Abnormality	Management Recommendations
Hyperuricemia	
Uric acid \geq 8.0 mg/dL (476 μ mol/L)	
 • Consider rasburicase (dose per institutional guidelines). 
 ○ If rasburicase is used, consider screening for G6PD deficiency prior to administration in patients at higher risk for G6PD deficiency (e.g., patients of African or Mediterranean ancestry) prior to starting rasburicase. Please refer to local label for tests to be performed, contraindications and precautions. • If rasburicase is used, sodium bicarbonate should not be used as this may exacerbate calcium phosphate precipitation. • Recheck potassium, phosphorus, uric acid, calcium and creatinine in 1 hour STAT.
Uric acid \geq 10 mg/dL (595 μ mol/L) OR Uric acid \geq 8.0 mg/dL (476 μ mol/L) with 25% increase and creatinine increase \geq 0.3 mg/dL (\geq 0.027 mmol/L) from pre-dose level	
 • Administer rasburicase (dose per institutional guidelines). • If rasburicase is used, consider screening for G6PD deficiency prior to administration in patients at higher risk for G6PD deficiency (e.g., patients of African or Mediterranean ancestry) prior to starting rasburicase. Please refer to local label for tests to be performed, contraindications and precautions. • If rasburicase is used, sodium bicarbonate should not be used as this may exacerbate calcium phosphate precipitation. • Notify nephrology (or other acute dialysis service). • Recheck potassium, phosphorus, uric acid, calcium and creatinine in 1 hour STAT. • If uric acid $<$ 8.0 mg/dL 1 hour later, repeat potassium, phosphorus, uric acid, calcium and creatinine 2 and 4 hours later, if no other evidence of tumor lysis.
Hypocalcemia	
Calcium \leq 7.0 mg/dL (1.75 mmol/L) AND Patient symptomatic (e.g., muscle cramps, hypotension, tetany, cardiac arrhythmias)	
 • Administer calcium gluconate 50 – 100 mg/kg IV slowly with ECG monitoring. • Telemetry. • Recheck potassium, phosphorus, uric acid, calcium and creatinine in 1 hour STAT. • If calcium normalized 1 hour later, repeat potassium, phosphorus, uric acid, calcium and creatinine 2 and 4 hours later, if no other evidence of tumor lysis. • Calculate corrected calcium and check ionized calcium if albumin low.

Abnormality	Management Recommendations
Hyperphosphatemia	
Phosphorus ≥ 5.0 mg/dL (1.615 mmol/L) with ≥ 0.5 mg/dL (0.16 mmol/L) increase	
 • Administer a phosphate binder (e.g., aluminum hydroxide, calcium carbonate, sevelamer hydroxide, or lanthanum carbonate). • Nephrology (or other acute dialysis service) notification (dialysis required for phosphorus ≥ 10 mg/dL). • Recheck potassium, phosphorus, uric acid, calcium and creatinine in 1 hour STAT. • If phosphorus < 5.0 mg/dL 1 hour later, repeat potassium, phosphorus, uric acid, calcium and creatinine 2 and 4 hours later, if no other evidence of tumor lysis.
Creatinine	
Increase $\geq 25\%$ from baseline	
 • Start or increase rate of IV fluids. • Recheck potassium, phosphorus, uric acid, calcium and creatinine in 1 – 2 hours STAT.

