5.2.3 Prior and Concomitant Therapy

Any medication or vaccine (including over-the-counter or prescription medications, vitamins and/or herbal supplements) that the subject is receiving at the time of enrollment, or receives during the study, must be documented in source documents and electronic case report forms (eCRFs) along with the reason for use, date(s) of administration including start and end dates, and dosage information including dose, route, and frequency.

The AbbVie Medical Monitor or designee (refer to Section 6.1.5) should be contacted if there are any questions regarding prior and concomitant therapies.

Vaccination with a live vaccine should be avoided. Killed or inactivated vaccines may be administered; however the response to such vaccines may be diminished. General guidelines regarding excluded, cautionary and allowed medications are summarized in [Table 1](#) and [Appendix I](#).

Table 1. Excluded Food/Medications

Excluded Food (from 3 Days Prior to Study Administration Until Last Day of Treatment)

 • Grapefruit and grapefruit products • Seville Oranges (including marmalade containing Seville oranges) • Starfruit
Excluded Drugs

 • Strong CYP3A inducers (During Ramp-Up and Throughout the Study)
Cautionary, Additional Guidance Noted

 • Strong and Moderate CYP3A Inhibitors[^] Consider alternative medications. If subject requires use of these medications, use with caution and reduce the venetoclax as described in Table 2. • Moderate CYP3A Inducers[^] Exclude during ramp-up phase and consider alternative medications. If subject requires use of these medications, use with caution and contact AbbVie Medical Monitor or designee (refer to Section 6.1.7) for guidance. • P-gp inhibitors Consider alternative medications. If subject requires use of these medications, use with caution and reduce the venetoclax dose by at least 2-fold (see Table 2).
Cautionary

 • Warfarin and coumarin derivatives* • P-gp substrates** • BCRP substrates • OATP1B1/1B3 substrates • BCRP inhibitors

[^] Chinese subjects are prohibited to take strong CYP3A inhibitors, moderate CYP3A inhibitors and inducers 7 days prior to the initiation of study treatment through the end of intensive PK collection (24 hours post dose on Cycle 1 Day 10).

* Closely monitor International Normalization Ratio (INR).

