** If a narrow therapeutic index P-gp substrate must be used, it should be taken at least 6 hours before venetoclax.

Table 2. Dose Modifications for Venetoclax: Moderate and Strong CYP3A Inhibitor Use

Assigned Venetoclax Dose	Modified Dose if Co-Administered with a Moderate CYP3A or P-gp Inhibitor	Modified Dose if Co-Administered with a Strong CYP3A Inhibitor
100 mg	50 mg	10 mg
200 mg	100 mg	20 mg
400 mg	200 mg	50 mg
600 mg	300 mg	50 mg

Note: After discontinuation of the inhibitor, wait for 2 to 3 days before venetoclax dose is increased back to the previous dose level. Ramp-up is not required upon discontinuation of the inhibitor.

A sample list of excluded medications and cautionary medications that fall into the categories within this section of the protocol can be found in [Appendix I](#). It is not possible to produce a comprehensive list of medications that fall into these categories, so if in question, please refer to the appropriate local product label and/or FDA website: <http://www.fda.gov/Drugs/DevelopmentApprovalProcess/DevelopmentResources/DrugInteractionsLabeling/ucm080499.htm> and notify the AbbVie Medical Monitor and discuss the investigator's intended use of these medications with the subject in question and the investigator's plans to medically monitor the potential study subject.

Commonly used anti-infective agents for prophylaxis (including ciprofloxacin and azole anti-fungal medications) and calcium channel blockers (diltiazem and verapamil) have CYP3A inhibitory properties and dose reductions of venetoclax/placebo are required.

Steroid therapy during study participation should be limited to lower dose and short duration if medically indicated. Intrathecal chemotherapy or radiation therapy for CNS prophylaxis is not permitted during study participation.

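### Appendix I flags P-gp inhibitors for at least a 4-fold venetoclax reduction, but Table 2, which it cites, gives exactly 2-fold

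*Protocol*

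**What the plan says.** Three places in the protocol deal with venetoclax dosing alongside a P-gp inhibitor.

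- **Appendix I** lists the drugs: "P-gp inhibitors† Amiodarone, captopril, carvedilol, dronedarone" and six more. The † footnote reads "use with caution and reduce the venetoclax dose by at least 4-fold (Table 2"). Strong CYP3A inhibitors also carry †. Moderate CYP3A inhibitors carry ‡, which reads "use with caution and reduce the venetoclax dose by at least 2-fold (Table 2").
- **Table 2 (Section 5.2.3)** fixes the doses in milligrams. P-gp inhibitors fall under the column "Modified Dose if Co-Administered with a Moderate CYP3A or P-gp Inhibitor". A separate column is headed "Modified Dose if Co-Administered with a Strong CYP3A Inhibitor".
- **Table 1 (Section 5.2.3)** says of P-gp inhibitors: "use with caution and reduce the venetoclax dose by at least 2-fold (see Table 2").

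Section 5.2.3 introduces Appendix I as "A sample list of excluded medications and cautionary medications that fall into the categories within this section of the protocol". Section 6.1.7 (Toxicity Management) names Table 1, Table 2 and Appendix I together as the places to look when reducing venetoclax or placebo for an interacting drug. None of the text supplied corrects the marker on the P-gp row.

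**The concern.** The † footnote sets a minimum reduction and names Table 2 as its source, yet the Table 2 column for P-gp inhibitors does not reach that minimum at any dose level. A site that reads both has two instructions it cannot satisfy together.

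The marker is not idle text. Tables 1 and 2 name the class but no P-gp inhibitor. Appendix I is the only place in the protocol that lists drugs as P-gp inhibitors, so a site checking amiodarone, carvedilol or ticagrelor will meet † there. At stake is a factor of two in the dose for a patient on one of these drugs. If Table 2 is right, literal use of † underdoses. If † was meant, Table 2 gives twice what is allowed. The instruction still applies after the final analysis, because Section 5.4.1 lets subjects continue on their assigned arm, subject to clinical benefit, commercial supply and the discontinuation criteria.

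**Working it through.** **Inputs.** Assigned and modified doses are from Table 2. The minimum reductions are from the † and ‡ footnotes of Appendix I.

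**Formulas.** Fold reduction = assigned dose / modified dose. Ceiling under † = assigned dose / 4. Excess = Table 2 P-gp dose / † ceiling.

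**Step 1: do the footnotes reproduce where they clearly belong?**

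- Strong CYP3A column, marked †: 100/10 = 10, 200/20 = 10, 400/50 = 8, 600/50 = 12. All are at least 4-fold, so † is met.
- Moderate CYP3A column, marked ‡: 100/50 = 200/100 = 400/200 = 600/300 = 2.0. All are at least 2-fold, so ‡ is met.

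**Step 2: does † reproduce for P-gp inhibitors?** They share the moderate column.

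| Assigned (mg) | Table 2 with P-gp inhibitor (mg) | Fold | † ceiling (mg) | Excess |
|---|---|---|---|---|
| 100 | 50 | 2.0 | 25 | 2.0 |
| 200 | 100 | 2.0 | 50 | 2.0 |
| 400 | 200 | 2.0 | 100 | 2.0 |
| 600 | 300 | 2.0 | 150 | 2.0 |

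It does not. The Table 2 dose is twice the † ceiling on every row.

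**Step 3: which entry is likely wrong?** With ‡ on the P-gp row, Appendix I would say at least 2-fold, which agrees with all four Table 2 rows and with Table 1. With † kept, the only Table 2 column that meets the footnote is headed for strong CYP3A inhibitors, not P-gp inhibitors. One symbol reconciles all three places.

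**Step 4: how many listed drugs are affected?** The P-gp row has 10 drugs. One (dronedarone) is also in the moderate CYP3A row and none is in the strong CYP3A row. So for 10 − 1 = 9 drugs, † is the only dose-reduction footnote in Appendix I.

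**The case against.** The strongest reply is that this is one small symbol and the protocol largely resolves it. The † footnote sends the reader to Table 2, whose column heading names P-gp inhibitors and gives a dose at each level. Appendix I is only a sample list. Section 5.2.3 says the Medical Monitor or designee "should be contacted if there are any questions regarding prior and concomitant therapies", and for drugs whose category is in question it adds a check of the local label or FDA website and a discussion with the Medical Monitor. Tables may also be misread when text is taken from a PDF. All of this stands and keeps the point minor. It does not remove it: the footnote's figure is still wrong for the table it cites, and † and ‡ are kept apart on the adjacent rows, which makes a misread less likely without excluding it.

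Four stronger readings are tempting and are not supported.

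- *Table 1 also contradicts †.* It does not. At least 2-fold is a minimum, and a 4-fold cut meets it. Table 1 favours ‡; the direct conflict is between † and Table 2.
- *Appendix I contradicts itself over dronedarone.* It does not, for the same reason: a 4-fold cut satisfies both footnotes.
- *Only 600 mg and 400 mg matter after ramp-up.* Table 7 ends at 400 mg, but Section 6.1.7 also allows re-initiation at an unspecified lower dose, and reductions for other events after discussion with the medical monitor.
- *Patients were underdosed and efficacy suffered.* The documents report no misdosing and give no count of patients on a P-gp inhibitor.

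**Conclusion.** Wrong as written, and minor. Appendix I assigns P-gp inhibitors a reduction of at least 4-fold and cites Table 2, which gives exactly 2-fold; the Table 2 dose is 2.0 times the † ceiling at every level (for example 300 mg against at most 150 mg at the 600 mg target). The marker is the likelier error, because ‡ agrees with Tables 1 and 2 and Appendix I is introduced only as a list of drugs within the categories of Section 5.2.3.

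This is an inconsistency between two parts of the protocol, not an objection to the dose in Table 2. It rests on two assumptions: that the original PDF shows † on the P-gp row, and that Table 2 is the intended dose, which the text supports but only the sponsor can confirm. The clinical effect cannot be sized from the documents. The OS comparison, its alpha and its power do not depend on it.

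**What to change.** 1. Check the symbol on the P-gp inhibitor row in the original PDF of Appendix I.
2. If it is †, ask the sponsor's clinical pharmacology group to confirm the 2-fold reduction, then change the marker to ‡.
3. Send sites a short note that Table 2 gives the venetoclax or placebo dose with any P-gp inhibitor.

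The cost is one footnote marker, which can go in as an administrative change, and a brief site communication. It needs no new data, no extra patients and no change to the SAP. If clinical pharmacology instead confirms 4-fold, Table 2 needs a separate P-gp column and Table 1 a matching minimum. That is a larger edit, and nothing in the documents points to it.

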Appendix K. Japan Specific Information

1.0 Clinical Expense and Compensation

Appendix L. Protocol Amendment: List of Changes

The summary of changes is listed in Section 1.1.

Specific Protocol Changes:

Section 1.2 Synopsis

Subsection Methodology:

Heading "Study Treatment"

Last paragraph, tenth sentence previously read:

Disease assessments should also occur at the Final Visit and any other time the patient features suggest relapse.

Has been changed to read:

Disease assessments should also occur at the Final Visit and any other time the patient features suggest relapse or progressive disease. For subjects who are unblinded following the final analysis results, bone marrow collection every 3 cycles starting at the end of Cycle 4 and bone marrow collection after CRi to confirm CR are not required. Bone marrow collection until 2 successive disease assessments resulting in CR or CRi is not required. Bone marrow collection can be completed as per institutional standard of care.

Section 1.2 Synopsis

Subsection Criteria for Evaluation:

Heading "Efficacy:"

First paragraph, sixth, seventh, and eighth sentence previously read:

For all subjects a bone marrow aspirate and biopsy must be performed at end of Cycle 4 and every 3 cycles (\pm 1 week) thereafter. Bone marrow aspirate and biopsy should also be performed upon concern for relapse and at the Final Visit (if no bone marrow was collected within the last 6 – 8 weeks, or if relapse of disease has already been confirmed). Bone marrow will be obtained until two successive samples indicate CR or CRi.

Has been changed to read:

For all subjects a bone marrow aspirate and biopsy must be performed at end of Cycle 4 and every 3 cycles (\pm 1 week) thereafter, however, these collections are not required for subjects who are unblinded following the final analysis results. Bone marrow collection can be completed as per institutional standard of care. Bone marrow aspirate and biopsy should also be performed upon concern for relapse or progressive disease and at the Final Visit (if no bone marrow was collected within the last 6 – 8 weeks, or if relapse or progression of disease has already been confirmed). Bone marrow will be obtained until two successive samples indicate CR or CRi, however, these collections are not required for subjects who are unblinded following the final analysis results.

Section 1.2 Synopsis

Subsection Criteria for Evaluation:

Heading "Efficacy:"

First paragraph, tenth sentence previously read:

For subjects with a response of CRi on two successive bone marrow samples an additional bone marrow aspirate and biopsy must be performed to confirm a CR once peripheral blood count recovery is noted.

Has been changed to read:

For subjects with a response of CRi on two successive bone marrow samples an additional bone marrow aspirate and biopsy must be performed to confirm a CR once peripheral blood count recovery is noted, however, these collections are not required for subjects who are unblinded following the final analysis results.

Section 5.1.3 Treatment Period

Subsection Cycle Length – 28 Days

Last paragraph

Add: new third, fourth and fifth sentence

For subjects who are unblinded following the final analysis results, bone marrow collections every 3 cycles starting at the end of Cycle 4 and bone marrow collection after

CRi to confirm CR are not required. Bone marrow collection until 2 successive disease assessments resulting in CR or CRi is not required for these unblinded subjects. Bone marrow collection can be completed as per institutional standard of care.

Section 5.3.1.1 Study Procedures

Subsection Bone Marrow Aspirate and Biopsy for Disease Assessments

First paragraph previously read:

Bone marrow aspirates and biopsies per Appendix C will be obtained for local assessment at the following time points until two successive samples indicate CR or CRi:

Has been changed to read:

Bone marrow aspirates and biopsies per [Appendix C](#) will be obtained for local assessment at the following time points until two successive samples indicate CR or CRi (bone marrow collection until two successive samples indicate CR or CRi is not required for subjects who are unblinded following the final analysis results):

Section 5.3.1.1 Study Procedures

Subsection Bone Marrow Aspirate and Biopsy for Disease Assessments

Fourth, fifth, and sixth bullet previously read:

- For subjects with a response of CRi on two successive bone marrow samples, an additional bone marrow aspirate and biopsy must be performed to confirm a CR once peripheral blood count recovery is noted.
- For all subjects a bone marrow aspirate and biopsy must be performed at end of Cycle 4 and every 3 cycles (\pm 1 week) thereafter.
- Upon concern for relapse.

Has been changed to read:

- For subjects with a response of CRi on two successive bone marrow samples, an additional bone marrow aspirate and biopsy must be performed to confirm a CR once peripheral blood count recovery is noted. This is not required for subjects who are unblinded following the final analysis results.

- For all subjects a bone marrow aspirate and biopsy must be performed at end of Cycle 4 and every 3 cycles (\pm 1 week) thereafter. This is not required for subjects who are unblinded following the final analysis results. Bone marrow aspirate and/or biopsy can be completed as per institutional standard of care.
- Upon concern for relapse or progressive disease.

Section 5.3.1.1 Study Procedures

Subsection Bone Marrow Aspirate and Biopsy for Disease Assessments

Fourth paragraph, third sentence previously read:

For these subjects, if a bone marrow aspirate sample is inadequate or un-evaluable, a repeat aspirate sample and biopsy must be performed within 7 days.

Has been changed to read:

For these subjects, if a bone marrow aspirate sample is inadequate or un-evaluable, a repeat aspirate sample and/or biopsy can be performed as per institutional standard of care.

Section 5.3.1.1 Study Procedures

Subsection Bone Marrow Aspirate and Biopsy for Disease Assessments

Fourth paragraph, fifth sentence previously read:

The corresponding protected health information (PHI) redacted local laboratory pathology report/bone marrow report should be sent to the central laboratory for each local disease assessment which is conducted.

Has been changed to read:

The corresponding protected health information (PHI) redacted local laboratory pathology report/bone marrow report should be sent to the central laboratory for each local disease assessment which is conducted, until otherwise instructed by the Sponsor.

Section 5.3.1.2 Collection and Handling of Biomarker and Exploratory Research Samples (Not Applicable for China)

Subsection Blood Collection for Plasma:

Third bullet

Add: new last sentence

For subjects who are unblinded following the final analysis results, sample collection every 3 cycles after end of Cycle 1 visit is not required.

Section 5.3.1.2 Collection and Handling of Biomarker and Exploratory Research Samples (Not Applicable for China)

Subsection Bone Marrow Collection for Disease Assessment by Flow Cytometry

Second bullet

Add: new second and third sentence

For subjects who are unblinded following the final analysis results, sample collection every 3 cycles after end of Cycle 1 visit is not required. Bone marrow aspirate completed as per institutional standard of care should continue to split for this assessment.

Section 5.3.1.2 Collection and Handling of Biomarker and Exploratory Research Samples (Not Applicable for China)

Subsection Bone Marrow Collection for Translational Research:

Add: new second and third sentence

For subjects who are unblinded following the final analysis results, sample collection every 3 cycles after end of Cycle 1 visit is not required. Bone marrow aspirate completed as per institutional standard of care should continue to split for this assessment.

Section 5.3.1.2 Collection and Handling of Biomarker and Exploratory Research Samples (Not Applicable for China)

Subsection Bone Marrow Aspirate and Biopsy Collections

Second bullet

Add: new fourth sentence

For subjects who are unblinded following the final analysis results, peripheral blood biomarker sample collection every 3 cycles after end of Cycle 1 visit is not required.

Section 5.3.3 Efficacy Variables

Subsection Reporting of Results

First paragraph

Add: new third and fourth sentence

For subjects who are unblinded following the final analysis results, assessments every 3 cycles thereafter are not required. Bone marrow collection can be completed as per institutional standard of care.

Section 5.4.1 Discontinuation of Individual Subjects from Treatment

Add: new fourth paragraph

Following the final analysis results, the subjects will be unblinded by the Sponsor to the treatment assignment and subjects will be allowed to continue the assigned treatment arm as long as they derive clinical benefit from the treatment in the opinion of the investigator, or until transition to commercial supply is available, or until protocol criteria for discontinuation is met.

Section 5.5.5.1 Blinding of Investigational Product

Add: new last paragraph

Following the final analysis results, the Investigator, the study site personnel, the subjects, and AbbVie personnel will be unblinded by the Sponsor to subjects' treatment assignment.

